### 6.11.2.3 Supplementary Analyses based on the Primary Endpoint

A number of supplementary analyses based around the primary endpoint will be undertaken. Different aspects of the endpoint, be they the calculation method, different data assumptions or different populations will be varied to assess the impact of each.

- Renal response at Week 52 will be derived programmatically and analyzed in an identical fashion to the primary analysis (Table 14.2.1.1.2). Using the same definition as given to the CEC and as set out in the primary endpoint section, renal response at week 52 will be derived programmatically. All components of the primary response endpoint will be independently programmed apart from the use of rescue medication. The CEC adjudication on the use of rescue medication will be incorporated into the programmed endpoint.
- The analysis described in Section 6.11.2 will be repeated for the PPS (Table 14.2.1.3).
- The analysis described in Section 6.11.2 will be repeated for each biopsy class category (Class III, Class III/V, Class IV, Class IV/V, Class V and Class VI). The combining of classes may be necessary should subject numbers in any individual class be deemed insufficient. A separate category defined as “All but Pure Class V” will be defined (Table 14.2.1.4).
- For both the adjudicated week 52 renal response (primary endpoint) and the programmed week 52 renal response (supplementary endpoint), each individual component (and some component groups) of the endpoint will be summarized by treatment group and analyzed in the same manner using a logistic regression. Analysis will be undertaken where possible, however, it is recognized that individual components may include very low numbers of subjects (either responders or non-responders). “eGFR success” is defined as an eGFR measure of  $\geq 60$  mL/min/1.73 m^2 *or* no confirmed decrease from baseline in eGFR of >20% *or* no disease-related or treatment-related AE impacting eGFR. Where data allows, the numbers of subjects achieving each of the following will be summarized (Table 14.2.1.5.1 (adjudicated) and Table 14.2.1.5.2 (programmed)):
  - UPCR  $\leq 0.5$  mg/mg

- eGFR success
- UPCr  $\leq 0.5$  mg/mg and eGFR success
- Received no rescue medication for LN
- No withdrawal prior to remission assessment
- Did not receive more than 10 mg prednisone equivalent for  $\geq 3$  consecutive days or for  $\geq 7$  days in total during Weeks 44 through 52, just prior to the renal response assessment
- “eGFR success” will also be summarized by individual components:
  - eGFR  $\geq 60$
  - eGFR  $< 60$  with no confirmed decrease  $> 20\%$
  - eGFR  $< 60$  with confirmed decrease  $> 20\%$  but with no disease-related or treatment-related eGFR associated AE present at time of assessment.

Confirmed decrease  $> 20\%$  in eGFR is two consecutive measurements, three or more days apart by the visit where response is defined.

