### **5.2 Inclusion Criteria**

The following inclusion criteria must be met for each subject:

1. Written informed consent before any study-specific procedures are performed.
2. Male or female subjects with a minimum age of 18 (or legal age of consent if >18 years) to 75 years of age, inclusive, at the time of screening (Visit 1).
3. Previous diagnosis of SLE according to the American College of Rheumatology criteria (1997; see [Appendix 5](#)).
4. Subjects with evidence of active nephritis, defined as follows:

Kidney biopsy result within 2 years prior to screening indicating Class III, IV-S, IV-G (alone or in combination with Class V), or Class V LN (see [Appendix 3](#)) with a doubling or greater increase of UPCR within the last 6 months to a minimum of  $\geq 1.5$  mg/mg for Class III/IV or to a minimum of  $\geq 2$  mg/mg for Class V at screening. Biopsy results over 6 months prior to screening must be reviewed with a medical monitor to confirm eligibility.

OR

Kidney biopsy result within 6 months prior to screening indicating Class III, IV-S, or IV-G (alone or in combination with Class V) LN with a UPCR of  $\geq 1.5$  mg/mg at screening.

OR

Kidney biopsy result within 6 months prior to screening indicating Class V LN and a UPCR of  $\geq 2$  mg/mg at screening.

A biopsy can be performed during screening, if not available. The above criteria must be fulfilled at baseline.

5. In the opinion of the Investigator, subject requires high-dose corticosteroids and immunosuppressive therapy.
6. Subject is willing to take oral MMF for the duration of the study, either by continuing current MMF therapy or by initiating it on or before the Baseline Visit.
7. Women of childbearing potential must have a negative serum pregnancy test at screening and a negative urine pregnancy test at baseline. Two effective forms of contraception must be used simultaneously unless abstinence is the chosen method. Subjects must use effective contraception during the study (see Section 5.4, [Adequate/Effective Contraception](#)).

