## 4 SAMPLE SIZE

The total sample size will be approximately 324 subjects (162 subjects per treatment arm). This is based on the following assumptions:

- A two group continuity corrected Chi square test with a 0.05 two-sided significance level will have 80% power to detect the difference between a placebo response rate of 20.0% and a voclosporin response rate of 34.4% (odds ratio=2.1) when the sample size in each group is 162 (total N=324).
- The effect of withdrawals will be investigated. Subjects withdrawing for any reason will be counted as non-responders in the primary analysis and therefore no adjustment of sample size for withdrawals is necessary.
- The impact of withdrawals on primary endpoint will be investigated in the tipping point analysis.

Table 4.1 shows the voclosporin response rates required to maintain a minimum 80% power at the planned sample size for given placebo response rates. These response rates all lead to odds ratios of around 2, which is a clinically relevant effect.

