## **5 RANDOMIZATION**

All subjects enrolled must be identifiable throughout the study. The Investigator will maintain a list of subject numbers and subject names to enable records to be found at a later date. Subjects will be allocated a subject number at the screening visit and registered with an interactive central randomization system. Subjects meeting the required eligibility criteria will be randomized to treatment at Visit 2 (baseline).

The randomization will be stratified by biopsy class (Class V only versus Others) and by prior MMF use at time of screening. The subjects will be randomized in a ratio of 1:1 to receive either voclosporin 23.7 mg BID or matching placebo. To help ensure balance, a centralized randomization will be utilized where region will be employed as a blocking factor. This will ensure balance between treatment groups within each of the 4 regions: North America, Latin America, Europe / South Africa and Asia Pacific.

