## 6.11.2 Primary Efficacy Analysis

### 6.11.2.1 Renal response at Week 52

Renal response at Week 52 will be adjudicated by the Clinical Endpoints Committee (CEC) and as such the analysis will incorporate the CEC's assessments of each subject. In order to perform their adjudication, the CEC will be provided UPCR data, eGFR data, steroid taper data, rescue and prohibited medication data and adverse event data. Full details of the adjudication process are detailed in a separate CEC Charter.

The primary efficacy analysis will be conducted on the ITT population using a logistic regression model with terms for treatment, baseline UPCR, biopsy class, MMF use at baseline and region, and renal response (Yes/No) at week 52 as the response variable (Table 14.2.1.1.2).

The results will be expressed as an odds ratio (and associated two sided- 95% CI) for voclosporin compared to placebo. Odds ratios greater than unity will mean the odds of response are greater for voclosporin than for placebo and therefore indicate a benefit of the voclosporin treatment arm. The p-value of the treatment effect will also be reported.

The following SAS program will be used for the primary efficacy analysis:

```
Proc Logistic data = data;  
Class Treatment_arm MMF_Use Biopsy_Class Region;  
Model Response = Treatment_arm MMF_Use Biopsy_Class Baseline_UPCR Region;  
Run;
```

The number of responders and non-responders at Week 52 will be summarized by treatment arm and a listing of renal responders and non-responders will also be provided.

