## 9 CHANGES TO PLANNED PROTOCOL ANALYSIS

In the randomization, regional differences were not expected and blocking by region was done more for drug distribution reasons. While the analysis specified in the protocol stipulated that the regional blocking factor was not to be used in the analysis models, following feedback from regulatory agencies, the models will include terms for each of the factors used in the randomization process:

- Biopsy Class (Class V versus Others)
- MMF use at screening (Yes versus No)
- Region (North America, Latin America, Europe+South Africa and Asia Pacific)

During the regulatory agency review and feedback process it was decided to remove the ‘Duration of UPCR  $\geq 0.5$ ’ endpoint from the list of key-secondary endpoints and place it within the list of ‘Other Secondary Endpoints’. The proportion of subjects experiencing a confirmed  $>30\%$  decrease from baseline in eGFR at each timepoint was also removed from the list of key secondary endpoints. To this end, neither endpoint will form part of the hierarchical testing procedure.

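### Class-specific odds ratios would be less inflated and more precise from one treatment-by-class model than from refitting the primary model within each biopsy class

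*SAP*

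**What the plan says.** SAP 6.11.2.3 states that the analysis of Section 6.11.2 "will be repeated for each biopsy class category (Class III, Class III/V, Class IV, Class IV/V, Class V and Class VI", with results in Table 14.2.1.4. It allows classes to be merged if numbers are judged too small, without giving a threshold or an order of merging, and it adds an All but Pure Class V category.

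The model being repeated is logistic, with "terms for treatment, baseline UPCR, biopsy class, MMF use at baseline and region". SAP 9 gives the class factor two levels, "Biopsy Class (Class V versus Others", and region four.

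SAP 6.11.2.2 plans a separate set of models on the same endpoint and ITT population. Each adds a treatment interaction with one factor, and biopsy class is one of the factors. The stated output is a p-value for the factor and one for the interaction (Tables 14.2.1.7.1-7). The section does not say how many levels biopsy class has there, or whether baseline UPCR, MMF use and region stay in the model.

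Protocol 5.2 admits "Class III, IV-S, or IV-G (alone or in combination with Class V) LN" and Class V alone. It does not list Class VI. Neither document gives expected numbers per class.

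**The concern.** Table 14.2.1.4 is the only place where the SAP promises a treatment effect for each histological class, and it obtains each one from a separate small regression. Every such regression spends parameters on UPCR, MMF use and region that could be estimated once from the whole trial. Maximum-likelihood logistic regression with few responders per parameter overstates effects and loses precision. A reader could then take a large OR in one small class as a real difference between classes when none exists. The interaction test in SAP 6.11.2.2 guards against that reading only in part, because it comes with no class-specific estimates.

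**Working it through.** **Inputs from the documents.** SAP 4: "The total sample size will be approximately 324 subjects (162 subjects per treatment arm"); "A two group continuity corrected Chi square test with a 0.05 two-sided significance level will have 80% power" for "a placebo response rate of 20.0% and a voclosporin response rate of 34.4% (odds ratio=2.1"). SAP 5: "The subjects will be randomized in a ratio of 1:1", four regions.

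**Inputs assumed, because the documents give none.** Class sizes, covariate effects, and a common true OR of 2.10 in every class.

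**1. Design figure.** The OR is (0.344/0.656)/(0.200/0.800) = 2.098. The continuity-corrected formula gives 163 per arm against the stated 162, and power at 162 is 79.9%. The design reproduces.

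**2. Parameters.** After the constant class term drops out, one within-class fit has 1 intercept + 1 treatment + 1 UPCR + 1 MMF + 3 region = 7 parameters. Over five classes that is 35. One model with class intercepts, class-specific treatment effects and shared covariates has 5 + 5 + 1 + 1 + 3 = 15.

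**3. Responders.** The average rate is (20.0% + 34.4%)/2 = 27.2%. Expected responders are 0.272 × 324 ≈ 88 overall, about 12 in a class of 45, 8 in 30 and 5 in 20. Responders per parameter are 88/35 ≈ 2.5 for separate fits and 88/15 ≈ 5.9 for one model.

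**4. Failures that neither model can repair.** With m = n/2 subjects per arm, the probability that an arm has no responders or only responders is 1 − [1 − 0.8^m − 0.2^m] × [1 − 0.656^m − 0.344^m]. For n = 20 (m = 10) this is 1 − 0.8926 × 0.9852 ≈ 12%. It is 41% at n = 10, 4% at n = 30 and 1% at n = 40.

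**5. Simulation over class sizes.** There were 1,500 trials of 324 subjects for each of four assumed class distributions, with 1:1 allocation within class and modest UPCR, MMF and region effects. The treatment OR counts as non-estimable if |log OR| > 6 or its SE > 10. Each cell shows separate fits v one interaction model. Geometric mean and SE are taken over trials where both are estimable.

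| Class size | Non-estimable | Geometric-mean OR | Median SE of log OR | P(OR > 10) |
|---|---|---|---|---|
| 12 | 80% v 29% | 1.49 v 1.58 | 2.14 v 1.28 | 14% v 5% |
| 20 | 30–32% v 8–11% | 2.05–2.18 v 1.81–1.87 | 1.52–1.54 v 1.05–1.06 | 15–16% v 6–7% |
| 30 | 6.5–7.5% v 3.1% | 2.58–2.74 v 2.12–2.19 | 1.10 v 0.87 | about 15% v 6% |
| 40 | 1.8–2.0% v 0.7–1.1% | 2.44–2.61 v 2.11–2.21 | 0.88–0.89 v 0.75–0.76 | 10–11% v 3–4% |
| 45 | 0.7–1.0% v 0.5–0.7% | 2.50–2.59 v 2.22–2.27 | 0.81–0.82 v 0.71 | 8% v 3.5–3.8% |
| 54 | 0.1–0.3% for both | 2.38–2.55 v 2.19–2.29 | 0.71–0.72 v 0.65 | 5–6% v 2% |
| 155–220 | 0% for both | 2.16–2.18 v 2.15–2.16 | 0.32–0.39 v 0.32–0.38 | 0.1% or less for both |

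At 20 or fewer the mean ORs are not a measure of bias, because the most extreme trials have been excluded as non-estimable.

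**6. Second set of assumptions.** Class shares of 12% (III), 12% (III/V), 45% (IV), 17% (IV/V) and 14% (V) give about 39, 39, 146, 55 and 45 subjects. Over 1,000 trials, for III, III/V and V in turn:
- Geometric-mean OR: 2.62 v 2.29, 2.56 v 2.23, 2.54 v 2.28.
- SD of log OR: 1.12 v 0.85, 1.08 v 0.80, 0.99 v 0.80.
- P(OR > 10): 11% v 5%, 9% v 3%, 8% v 4%.

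Interval coverage was near nominal under both methods.

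**The case against.** The class sizes are not in the documents, and in large classes the choice of method makes no difference. The SAP allows sparse classes to be merged, and merging is an ordinary remedy. It already tests treatment by biopsy class in SAP 6.11.2.2. With near-nominal coverage, a wide interval is an honest picture of a 45-subject subgroup, and at that size the proposed model narrows the median SE only from about 0.82 to 0.71. It also imposes common covariate effects across classes and does nothing for an arm without responders. All of this stands, and it limits the point to inflation and avoidable loss of precision in small to moderate classes.

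Three stronger readings are tempting, and the documents do not support them:

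- **The model cannot be fitted.** A covariate that is constant within a subgroup carries no information and drops out. The SAP should say so, but this is a point of wording.
- **The table will often have missing ORs.** Some coefficient, usually a region term, does separate often: in 35% of fits at n = 39, 25% at n = 45 and 17% at n = 55 under the second set of assumptions. The treatment OR itself is non-estimable in only 1.9%, 0.7% and 0.3% of those fits, and it is the treatment OR that the table reports.
- **Listing Class VI is an error.** The ITT population is all randomized subjects, so a subject enrolled in deviation from the criteria could carry that class. The list and the eligibility criteria need reconciling, no more.

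**Conclusion.** The point holds as a cheap improvement. For assumed classes of about 39 to 55 subjects with no true heterogeneity, separate fits give a geometric-mean OR of about 2.4–2.6 where the truth is 2.10, against about 2.1–2.3 from one model. The SD of log OR at 39 to 45 subjects is about 1.0–1.1 against 0.80–0.85, and an OR above 10 is at least twice as likely. Non-estimable treatment ORs become common only at about 20 subjects or fewer, where the single model reduces them (30–32% to 8–11% at n = 20) without removing them. At about 150 or more there is nothing to choose between the methods.

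The sizes rest on assumed class numbers, assumed covariate effects and a common OR. The direction was the same under both sets of assumptions. The table is supplementary and outside the Hochberg procedure, so neither the primary result nor type I error is touched.

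**What to change.** In SAP 6.11.2.3, replace the within-class refits by an extension of the interaction model already planned in SAP 6.11.2.2:

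- Fit one ITT logistic model with treatment, biopsy class (III, III/V, IV, IV/V, V), treatment by class, and shared baseline UPCR, MMF use and region terms. State the class levels and the retained covariates in SAP 6.11.2.2 as well.
- Report the class-specific ORs with 95% CIs from it in Table 14.2.1.4, beside responder counts per arm and the interaction p-value.
- Take the All but Pure Class V estimate from the same model with the two-level class factor.
- Where an arm of a class has no responders or only responders, use Firth penalisation or show counts only. If merging of classes is kept, give its trigger and order before unblinding.
- Reconcile the Class VI category with Protocol 5.2.

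The cost is a few lines of SAP text and one model statement, with no new data. The price is the assumption that covariate effects are common across classes, which the primary model in SAP 6.11.2.1 already makes.

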#### **6.11.2.4 Tipping point analysis for primary endpoint (CEC adjudicated Renal Response)**

The impact of withdrawals on the primary endpoint will be investigated in a tipping point analysis where subjects whose response assessment was assumed due to missing data (missing data always results in a non-response assessment) will have their assessment re-assigned in a series of analyses that are progressively more in favor of placebo. Assuming that the primary analysis is significantly in favor of voclosporin, at some point, the series of analyses in the tipping point analysis is likely to show a lack of significance. It is of interest to assess how extreme the assumptions have to be around the subjects with missing data before primary significance is lost.

The tipping point analysis will consider the full range of possible response rates in the subjects with missing data in the primary analysis. This will be done by systematically changing assumed response rates from 0% to 100% in a stepwise manner. The imputation will be performed independently within the two treatment groups so that, in the most extreme case, the imputed response rate in the voclosporin arm will be 0% and 100% in the Placebo arm.

Multiple imputation will be used for each pair of response rates under consideration. Both the imputation model and the analysis model will incorporate the covariates as used in the primary analysis: Treatment arm, MMF use at screening, Biopsy Class, Baseline UPCR and Region. The combined results for each pair of response rates will be displayed graphically with the vertical axis being imputed placebo response (0 to 100%) and the horizontal axis being imputed voclosporin response (0 to 100%). Such a graph will be a comprehensive map of p-values using all plausible assumptions about missing outcomes and will provide a contour between significance and non-significance.

The following algorithm will be used for the imputation;

Step 1: Use efficacy data to identify subjects classed as non-responders due to missing data.

Step 2: 441 pairs of response rates for voclosporin and placebo in the table below will be used for the imputation.

		1	2	3	4	5	6	7	8	9	10	11	12	13	14	15	16	17	18	19	20	21
Placebo Response Rate (Y)	.95	22	23	24	25	26	27	28	29	30	31	32	33	34	35	36	37	38	39	40	41	42
	.9	43	44	45	46	47	48	49	50	51	52	53	54	55	56	57	58	59	60	61	62	63
	.85	64	65	66	67	68	69	70	71	72	73	74	75	76	77	78	79	80	81	82	83	84
	.8	85	86	87	88	89	90	91	92	93	94	95	96	97	98	99	100	101	102	103	104	105
	.75	106	107	108	109	110	111	112	113	114	115	116	117	118	119	120	121	122	123	124	125	126
	.7	127	128	129	130	131	132	133	134	135	136	137	138	139	140	141	142	143	144	145	146	147
	.65	148	149	150	151	152	153	154	155	156	157	158	159	160	161	162	163	164	165	166	167	168
	.6	169	170	171	172	173	174	175	176	177	178	179	180	181	182	183	184	185	186	187	188	189
	.55	190	191	192	193	194	195	196	197	198	199	200	201	202	203	204	205	206	207	208	209	210
	.5	211	212	213	214	215	216	217	218	219	220	221	222	223	224	225	226	227	228	229	230	231
	.45	232	233	234	235	236	237	238	239	240	241	242	243	244	245	246	247	248	249	250	251	252
	.4	253	254	255	256	257	258	259	260	261	262	263	264	265	266	267	268	269	270	271	272	273
	.35	274	275	276	277	278	279	280	281	282	283	284	285	286	287	288	289	290	291	292	293	294
	.3	295	296	297	298	299	300	301	302	303	304	305	306	307	308	309	310	311	312	313	314	315
	.25	316	317	318	319	320	321	322	323	324	325	326	327	328	329	330	331	332	333	334	335	336
	.2	337	338	339	340	341	342	343	344	345	346	347	348	349	350	351	352	353	354	355	356	357
	.15	358	359	360	361	362	363	364	365	366	367	368	369	370	371	372	373	374	375	376	377	378
	.1	379	380	381	382	383	384	385	386	387	388	389	390	391	392	393	394	395	396	397	398	399
	.05	400	401	402	403	404	405	406	407	408	409	410	411	412	413	414	415	416	417	418	419	420
	0	421	422	423	424	425	426	427	428	429	430	431	432	433	434	435	436	437	438	439	440	441
		0	.05	.1	.15	.2	.25	.3	.35	.4	.45	.5	.55	.6	.65	.7	.75	.8	.85	.9	.95	1
		Voclosporin Response Rate (X)																				

For each of the 441 pairs of response rates in the table above, (e.g., for pair number 255, response rate for voclosporin = 0.1, while response rate for placebo = 0.4.):

- For each subject identified in Step 1, generate a continuous response score between 0 (non-response) and 1 (response) using SAS proc mi adjusting for the covariates of treatment group, biopsy, MMF use at screening, baseline UPCR and region. Example SAS code is given below.
- Assign the imputed response (1 = response, 0 = non-response) based on the response score and the current tipping point. Using the example values above:
  - Given a voclosporin tipping point response rate of 0.1, subjects in the voclosporin group with a response score  $\geq 0.9$  would be imputed as responders and non-responders otherwise.
  - Given a placebo tipping point response rate of 0.4, subjects in the voclosporin group with a response score  $\geq 0.6$  would be imputed as responders and non-responders otherwise.

Example SAS code for the generation of a response score on the continuous scale (between 0 and 1):

```
proc mi data=impute01 out=impute20 nimpute=50 seed=3435 minimum=0 maximum=1;
  class TREATMENT BIOPSY MMF REGION;
  fcs nbiter=10 reg(RESPONSE = TREATMENT BIOPSY MMF UPCR REGION);
  var RESPONSE TREATMENT BIOPSY MMF UPCR REGION;
run;
```

For example, consider the case where 7 subjects (4 voclosporin, 3 placebo) in the data are considered non-responders due to missing data. Using the response rate number 299 (voclosporin = .2, placebo = .3)

Subject	Treatment	Continuous Response Score	Response Rate	Imputed Response
1	VCS	0.728119	.2	0
2	VCS	0.876749	.2	1
3	VCS	0.345234	.2	0
4	VCS	0.784817	.2	0
5	Placebo	0.923842	.3	1
6	Placebo	0.546724	.3	0
7	Placebo	0.734184	.3	1

Replace the response observed for the subjects in Step 1 (which, by definition, will be non-response) with their imputed data.

Step 3: Run the analysis of the primary endpoint (including stratification covariates) using the data in step 2. Repeat the imputation (step 2) and analyze 50 times to generate 50 individual odds ratios.

Step 4: Use Proc Mianalyze in SAS to pool the 50 odds ratios and output a common p-value.

Repeat Step 1 to 4 for all 441 pairs of response rates.

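### The tipping-point map labels its axes as imputed response rates, but its score threshold generally imputes fewer responders than the label says, more so for placebo

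*SAP*

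**What the plan says.** SAP 6.11.2.4 varies the assumed response rate among subjects with missing outcomes from 0% to 100% in steps of 5 points, separately by arm, giving a 21 × 21 grid of 441 pairs. The p-value map has "the vertical axis being imputed placebo response (0 to 100%) and the horizontal axis being imputed voclosporin response (0 to 100"%). In the worst corner, "the imputed response rate in the voclosporin arm will be 0% and 100% in the Placebo arm". The stated purpose is: "It is of interest to assess how extreme the assumptions have to be around the subjects with missing data before primary significance is lost".

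The score comes from "proc mi data=impute01 out=impute20 nimpute=50 seed=3435 minimum=0 maximum=1" with "fcs nbiter=10 reg(RESPONSE = TREATMENT BIOPSY MMF UPCR REGION"), which is a linear regression on a 0/1 outcome. The next instruction is "Assign the imputed response (1 = response, 0 = non-response) based on the response score and the current tipping point". The example that follows uses a cut-off of 0.9 for an assumed rate of 0.1, so the rule is: responder if the score is at least 1 minus the rate. The primary analysis is then rerun on each of 50 imputations and the results are pooled.

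The SAP does not calibrate the score, does not ask for the realised rates to be reported, and does not say what happens to draws outside 0–1.

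**The concern.** If a score is uniform on 0–1, the chance that it is at least 1 − r is exactly r, and the axis label is right. A linear-regression draw is roughly normal around the predicted response probability. At design rates of 20.0% and 34.4% its mean lies well below one half, so after bounding it leans towards zero. Fewer subjects pass the cut-off than the label claims, and the shortfall is larger for placebo, whose mean is lower.

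A placebo shortfall makes the result look harder to overturn, while a voclosporin shortfall works the other way. What is at stake is the distance the reader takes from the map: how high the placebo rate among missing subjects must be before significance goes.

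**Working it through.** **Inputs.** SAP section 4 gives 162 per arm and response rates of 20.0% and 34.4%. Its sample size reproduces: the uncorrected n is 148.7 per arm; with difference 0.144 the continuity-corrected n is (148.7/4) × (1 + √(1 + 4/(148.7 × 0.144)))² = 162.3, against 162 stated.

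Assumed, because the documents do not say: the missing counts and the handling of out-of-range draws. The base case has 16 missing per arm (9.9%) and 32 v 56 responders (19.8% and 34.6% of 162). Observed-case means are 32/146 = 0.219 and 56/146 = 0.384. The common SD is √[(0.219 × 0.781 + 0.384 × 0.616)/2] = 0.451.

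**Realised rates.** If out-of-range draws are redrawn, the realised rate at axis value r is

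[Φ((1−μ)/σ) − Φ((1−r−μ)/σ)] / [Φ((1−μ)/σ) − Φ(−μ/σ)].

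- Placebo, r = 0.40: (0.9582 − 0.8005)/(0.9582 − 0.3137) = 24.5%.
- Voclosporin, r = 0.40: (0.9140 − 0.6842)/(0.9140 − 0.1978) = 32.1%.

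| Axis value | Placebo realised | Voclosporin realised |
|---|---|---|
| 20% | 8.9% | 12.9% |
| 40% | 24.5% | 32.1% |
| 50% | 34.9% | 43.6% |
| 80% | 73.7% | 79.8% |

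The largest gaps are 15.6 points for placebo (at 42%; 0.156 × 16 ≈ 2.5 subjects) and 8.3 for voclosporin (at 32%). The 0% and 100% edges are exact. Near the top, voclosporin slightly exceeds its label (90.6% at 90%).

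If draws are clipped to 0 or 1 instead, the realised rate is 1 − Φ((1−r−μ)/σ) for r below 1. Axis 0/40/80% then gives 4.2/19.9/51.7% for placebo and 8.6/31.6/65.8% for voclosporin.

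With redrawing, the largest gaps shrink as observed-case rates rise: 10.8 and 5.0 points at 30%/45%, 8.5 and 3.2 at 35%/50%, 6.5 and 1.8 at 40%/55%. If the design rates are taken as the observed-case rates themselves (SD 0.439), the gaps are larger: about 17 and 10.5 points.

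**Effect on the contour.** Sixty datasets were simulated per scenario, with 32 v 56 responders and assumed covariate distributions. The SAP rule with redrawing was compared with logistic imputation on the same covariates, its intercept shifted within arm so that the mean probability equals the axis rate. Both used 50 imputations, the adjusted logistic model and Rubin pooling of log odds ratios. The tipping point is the first placebo axis value without significance in favour of voclosporin. Entries are the SAP rule minus the comparator in points on the placebo axis, median (range).

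| Missing, placebo/voclosporin | Voclosporin axis 0% | 20% | 40% |
|---|---|---|---|
| 8/8 | 5 (0 to 20); 30 of 60 tip | not tabulated | not tabulated |
| 16/16 | 10 (5 to 20) | 5 (−5 to 10) | 0 (−10 to 10); 57 tip |
| 24/24 | 15 (10 to 20) | 5 (0 to 10) | 5 (0 to 10) |
| 32/32 | 10 (5 to 15) | 10 (0 to 15) | 5 (0 to 10) |
| 16/32 | 10 (5 to 20) | −5 (−10 to 5); 52 tip | 1 of 60 tips |
| 32/16 | 15 (10 to 20) | 10 (5 to 15) | 10 (5 to 15) |

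Median cells of 441 significant only under the SAP rule v only under the comparator: 8/8, 0 v 0 (net change the other way in 18 of 60); 16/16, 8 v 4; 24/24, 15 v 0; 32/32, 20 v 0; 16/32, 5 v 4; 32/16, 39 v 0. Under clipping, the 16/16 shift at voclosporin 0% is 35 points (20 to 45).

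The comparator returned 39.8% and 40.1% at axis 40%. Covariate-free Bernoulli draws at the axis rate differed from it by a median of 3 cells at 16/16 and 5 at 32/32, which points to the rate error rather than the covariates.

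**The case against.** The strongest reply is that this is a sensitivity display and its key points survive. With redrawing, the cell with both rates at 0% is the primary analysis and is correct, as is the worst corner. That stands. The contour, however, is read mostly between the edges.

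Second, the effect is concentrated where voclosporin is assumed low. With equal missingness of 10–15% it is about one grid step at voclosporin 20%, and at about 5% missing it largely vanishes. SAP 3.1 expects subjects who stop study drug to stay in follow-up, so missingness may be low. This limits the size of the shift but does not make the labels right, because the gap in realised rates comes from the score distribution.

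Third, the contour results depend on the response rates too. In a treatment-only check at 16/16 and voclosporin 0%, the shift falls from 10 points with 32 v 56 responders to 5 with 57 v 81 and 0 with 65 v 89. That is a fair limit, although 20.0% and 34.4% are the plan's own rates.

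Fourth, clipping contradicts the 0% voclosporin corner that the SAP describes, so the clipped figures deserve little weight. They justify one clarifying sentence.

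Smaller points also stand. The reversal at 16/32 is one grid step at one axis value. The Bernoulli comparison favours the rate error on medians, but its range at 16/16 (0–13 cells) overlaps the plan's discordance. The text says imputation is done independently within arms, while the example code, followed here, fits one model across arms. Arm-specific SDs would move placebo at axis 40% from 24.5% to 22.2%.

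**Conclusion.** The concern holds: as written, the rule does not deliver the rates on the axes. At the design rates, with 16 missing per arm and redrawing, the shortfall reaches 15.6 points for placebo and 8.3 for voclosporin. In the part of the map most adverse to voclosporin, about 10–20% missing puts the displayed placebo tipping rate about 10–15 points too high. With equal missingness the shift fades as the assumed voclosporin rate rises. It persists if placebo has more missing, and changes sign at voclosporin 20% if voclosporin has more.

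These sizes rest on assumed missing counts, redrawing, assumed covariate distributions and the design response rates. The direction of the rate error at those rates does not depend on the missing rate. The primary test and type I error are untouched. This should be fixed, but it does not threaten the primary conclusion.

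**What to change.** Replace the threshold step with logistic imputation that keeps the primary-model covariates, as the SAP intends ("Both the imputation model and the analysis model will incorporate the covariates as used in the primary analysis"). Add an intercept shift in each arm, calibrated so that the mean imputed probability among missing subjects equals the axis rate. Calibrating the score cut-off within arm is an alternative. In either case, report the realised imputed rates beside the axis values. Covariate-free Bernoulli draws at the axis rate can serve as a check.

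If the threshold is kept, state how out-of-range scores are handled and label the map with realised rates.

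Two clerical corrections in the same section: the placebo example names the voclosporin group, and Step 4 should say that log odds ratios with their standard errors are pooled.

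The cost is SAP wording and slightly more programming. The contour may become less favourable where the voclosporin rate is assumed low.
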